- 0. Summary of baseline demographic and clinical characteristics separated by ertugliflozin group and placebo group will be generated. Significance testing between-group will be performed. The following variables will be included:
 - *Age, sex, weight, waist circumference, BMI, HbA1c, hemoglobin, fasting blood glucose*
 - race (white/black/Hispanic/Asian/other)
 - SBP, DBP, HR
 - Mean eGFR
 - UACR (median and IQR)
 - Concomitant medication (ACEi, ARB, Diuretic, statin)

1. Analysis for the primary objective:

- 1.1. To assess ertugliflozin-related acute and chronic changes in the primary outcome FE(Li+) compared to placebo, linear mixed-effects models will be used. Two separate models will be fit. For acute change, the vector of outcomes will include the baseline and 1-week values (i.e. Visit 3 and Visit 4 values). For chronic changes, the vector of outcomes will include the baseline and 12-week values (i.e. Visit 3 and Visit 8 values). The covariates will include the visit and treatment-by-visit interaction; due to randomization, a covariate for the main effect of treatment will not be included. The treatment-by-time coefficient, its 95% confidence interval, and its p-value will be used to assess the effect of treatment.
- 1.2. We will repeat this analysis with:
 - a. FE(Na+) as an outcome
 - b. FE(Na+) FE(Li+) as an outcome
- 1.3. In exploratory analysis to determine the overall effect of ertugliflozin across all timepoints, we will repeat the above analysis with one model where the vector of outcomes will include all data collected at baseline, 1-week, and 12-week values.

2. Analysis for secondary objective:

- 2.1. Linear regression will be performed with change in volume as the dependent variable and change in FE(Li+) as the independent variable, with treatment as a covariate. Two separate models will be fit for acute and chronic changes. Acute changes will use the baseline and 1-week values for both the dependent and independent variable values; chronic changes will use baseline and 12-week values.
- 2.2. The same models described in the analysis of secondary objective 2.1 will be completed, with changes in PV or ECF as independent predictors, for neurohormones as the dependent variables/outcomes.
- 2.3. 2.6. The same models described in the analysis of primary objective 1.1 and 1.3 will be completed for each of the different outcomes.

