- 2.7.The numbers of hypoglycemic events and serious adverse events will be reported for both the placebo group and ertugliflozin group. No statistical comparisons will be performed.

3. Analysis for exploratory objective:

- 3.1.– 3.3. The same models described in the analysis of primary objective 1.1 and 1.3 will be performed for each of the different outcomes.
- 3.4. The same models described in the analysis of secondary objective 2.1 will be completed, with changes in neurohormones as independent predictors, for changes in absolute measure of renal function as the dependent variables/outcomes.
- 3.5. The same models described in the analysis of secondary objective 2.1 will be completed, with changes in neuro-hemodynamic markers as independent predictors and changes in arterial stiffness as the different dependent variables/outcomes.

- 3.6. The same models described in the analysis of secondary objective 2.1 will be completed, with changes in neurohormones as independent predictors and changes to blood pressure as dependent variable/outcome.
- 3.7.– 3.8. The same models described in the analysis of primary objective 1.1 and 1.3 will be completed for each of the different outcomes.

Analysis population: The intention to treat population will be used for all analyses. There are no planned subgroup analyses for the primary outcome.

Hypothesis testing: For hypothesis testing, a 5% significance level will be used (two-sided). No interim analyses will be performed. For secondary objectives, nominal p-values will be reported.

General model assumptions and model diagnostic procedures: For the linear mixed-effects models with visit and treatment-by-visit interaction as covariates, a participant-level random intercept will be included. Restricted-maximum-likelihood will be used for estimation and the missing-at-random framework will be assumed. Plots of marginal and conditional residuals will be used for model diagnostics and assessment. Similar diagnostic procedures will be used for the linear regression models.

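### The 12-week primary model leaves out the week-1 data, and its random intercept assumes equal variance before and after treatment

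*SAP*

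**What the plan says.** SAP Analysis 1.1 treats the 1-week and 12-week effects on FE(Li) as separate fits: "Two separate models will be fit". The first uses Visits 3 and 4. For the second: "For chronic changes, the vector of outcomes will include the baseline and 12-week values (i.e. Visit 3 and Visit 8 values". The fixed effects are visit and treatment-by-visit, and "due to randomization, a covariate for the main effect of treatment will not be included", so both arms share one baseline mean.

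The SAP paragraph on general model assumptions gives the only covariance term: "a participant-level random intercept will be included". It adds that "Restricted-maximum-likelihood will be used for estimation and the missing-at-random framework will be assumed". Residual plots are planned, but no action is stated if the variances differ.

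Analysis 1.3 puts all three visits in one model, introduced by "In exploratory analysis to determine the overall effect of ertugliflozin across all timepoints". No other covariance is given for it. Analyses 2.3-2.6, 3.1-3.3 and 3.7-3.8 reuse models 1.1 and 1.3.

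On incomplete follow-up, the protocol (Visit 7 and 8) foresees stopping before week 12 and seeks a physiological assessment on the last day of product. Section 6.5 allows replacement after treatment has begun. No dropout rate is given.

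**The concern.** Two features of the primary model deserve attention, and they have different causes.

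(a) Every patient who reaches Visit 4 has a measured week-1 response, but the 12-week model never sees it. If Visit 8 is then missing, the patient is represented by a baseline alone. Missing at random then has to hold given baseline, although a more informative measurement exists. If the chance of leaving depends on the week-1 response, the 12-week estimate is biased.

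(b) A random intercept with a single residual variance implies the same variance at both visits. The drug is expected to move the mean by 40%, so the spread may move too. If it does, the standard error and the confidence interval are wrong.

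**Working it through.** **Inputs from the documents.** Protocol, sample size calculation: baseline 22, SD 7, 40% increase, 18 per group. The effect is 0.40 × 22 = 8.8. The plan gives no figure for post-treatment spread, coverage or dropout, so there is none to reproduce on this point. (The stated sample-size inputs give 10 per group by the normal formula, not 18. That is a separate matter and does not bear on this one.)

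**Assumed inputs.** Dropout of 0-20%, or 2-4 of 18 per arm; correlations between visits as shown; post-treatment SD of 0.7 to 1.4 times baseline.

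**(a) Week-1 data.** The two-visit model was compared by simulation with a three-visit unstructured model, both with a common baseline mean (3,000 trials per case, correlation of baseline with each later visit 0.5). Entries are the variance of the 12-week estimate, three-visit divided by two-visit:

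| Week-1/week-12 correlation | No dropout | 10% random | 20% random |
|---|---|---|---|
| 0.5 | 1.00 | 1.00 | 1.00 |
| 0.7 | 1.01 | 0.98 | 0.95 |
| 0.85 | 1.02 | 0.92 | 0.87 |

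Next, let dropout depend on week 1. The patients with the highest week-1 values leave the ertugliflozin arm (correlations 0.5, 0.5 and 0.7; 4,000 trials):

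| Lost per arm | Two-visit mean | Shortfall from 8.8 |
|---|---|---|
| 2 | 8.18 | 0.62 (7%) |
| 3 | 7.87 | 0.93 (11%) |
| 4 | 7.61 | 1.19 (14%) |

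The three-visit unstructured model gives 8.80-8.81. In a second scenario, treated patients drop out with a probability that rises with the week-1 value, and placebo patients at 5%. The two-visit mean is then 8.20, 7.77 and 7.45 for week-1/week-12 correlations of 0.5, 0.7 and 0.85, against 8.77-8.83 for the joint model.

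**(b) Equal variance.** Let s0 and s1 be the SDs before and after treatment, c their covariance and n the number per arm. The random-intercept model works with s² = (s0² + s1²)/2 and r = c/s². The estimate is the arm difference at follow-up minus r times the arm difference at baseline.

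- True variance: (2/n)(s1² − 2rc + r²s0²).
- Put c = rs² and s0² = 2s² − s1². The bracket becomes s1² − 2r²s² + 2r²s² − r²s1² = s1²(1 − r²).
- Model variance: (2/n)s²(1 − r²).
- True/model = s1²/s² = 2s1²/(s0² + s1²). The correlation cancels.

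If the arms differ after treatment, s1² is the mean of the two post-treatment variances. With s0 = 7:

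| Post-treatment SD | Variance ratio | SE ratio | Coverage, formula | Coverage, simulated |
|---|---|---|---|---|
| 7 in both arms | 1 | 1.00 | 95% | 94.7-95.3% |
| 9.8 treated, 7 placebo | 2 × 72.52/(49 + 72.52) = 1.19 | 1.09 | 92.7% | 92.5-93.0% |
| 4.9 in both arms | 2 × 24.01/(49 + 24.01) = 0.66 | 0.81 | 98.4% | 98.0-98.5% |

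Here 72.52 = (49 + 96.04)/2. The 9.8 is 7 × 1.4, which holds if the SD grows in proportion to the mean. Simulation: 18 per arm, 3,000 trials, REML, correlation 0.3 or 0.6. An analysis that leaves the variances free (checked as baseline-adjusted ANCOVA at the visit) kept 94.5-95.5% throughout.

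**The case against.** **The sizes are assumed.** The documents do not say why strong natriuretic responders would leave, and patients who stop early are to be measured on their last day of product. This stands as a limit on weight. It does not remove the point, because the SAP does not say whether a last-day value enters as Visit 8.

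**The harm is modest even in the adverse scenario.** A REML rerun with random losses in placebo gave 8.1, 7.9 and 7.6, with a model SE of 2.1-2.2, coverage of 95%, 94% and 92%, and power of 96%, 94% and 91%. The bias is about a third to a half of one SE, towards the null. This is correct for that dropout pattern.

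**A three-visit model is already planned.** In that rerun a three-visit random-intercept model gave 8.5, 8.5 and 8.4, so 1.3 would recover part of the loss. It is exploratory, however, and aimed at an overall effect. One random intercept also forces a single variance and a single correlation on all three visits. In that respect the two separate fits are less restrictive.

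**Imputation could bring week 1 back.** Protocol section 8.2 mentions multiple imputation, but under other study parameters and without naming the imputation variables. The SAP does not carry it over.

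**Stronger readings to avoid.** A reader might infer that splitting the models causes the equal-variance assumption. It does not; the random intercept does. A reader might also infer that the intervals are always too narrow. They are too narrow only if the SD rises, and the documents do not say which way it moves. Nor do the documents support an inflated type I error. If the SD rises because the treated mean rises, then under the null neither rises, and a simulation gave 5.3%. Real inflation would need the SD to rise in placebo as well, for which the documents give no reason.

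**Conclusion.** Both points hold on the text and are worth correcting, but neither shows the primary result to be unsound.

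(a) The 12-week estimate conditions on baseline only. Nothing is lost with complete data and little with random dropout. Bias arises only if Visit 8 values are missing in a way related to the week-1 response. The range of about 7.6-8.2 against 8.8 belongs to one assumed pattern, with 2-4 high responders lost from the ertugliflozin arm.

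(b) The interval is correct only if the SDs before and after treatment are equal. The formula is exact for the two-visit model, but its input is unknown: the documents give a baseline SD and no post-treatment SD. Coverage of about 92.5-93% and of about 98% shows that the error can go either way.

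**What to change.** Make the primary analysis one model on Visits 3, 4 and 8:

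- visit and treatment-by-visit terms, with no treatment main effect, as already planned;
- an unstructured within-patient covariance in place of the random intercept;
- REML with Kenward-Roger degrees of freedom;
- the Visit 4 and Visit 8 treatment contrasts taken from this model.

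Both changes are needed, since merging the visits under a single random intercept, as in 1.3, leaves the variance constraint in place. Use the same structure for the outcomes that reuse model 1.1. State also whether a last-day assessment counts as Visit 8. A by-product is a confidence interval for the difference between the week-1 and week-12 effects, which bears on the persistence named in the primary objective and which two separate fits cannot give.

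The cost is SAP wording and no new data. The model has six covariance parameters instead of two, with 36 patients, so pre-specify a fallback for non-convergence that still allows visit-specific variances, such as heterogeneous compound symmetry (four parameters).

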Current Management Strategies in Patients with HF: HF is characterized by activation of the SNS and renin angiotensin aldosterone system (RAAS) as counter-regulatory responses to maintain blood pressure and preserve renal function. Treatment of HF patients with reduced left ventricular ejection fraction (HFrEF, ejection fraction <45%) includes β -blockers and RAAS inhibitors, diuretics and digoxin to suppress neurohormones, reduce volume overload and improve cardiac contractility¹¹. In HFrEF, RAAS inhibitors reduce hospitalizations and mortality¹¹. In contrast, these therapies have failed to produce beneficial effects in patients with HF and *preserved* EF ("HFpEF", ejection fraction \geq 45%), which is a common type of HF in T2D¹¹. Accordingly, HFpEF management focuses on the treatment of co-morbidities (hypertension, coronary disease, obesity, hyperglycemia) ¹². Many of the comorbidities associated with HFpEF can be ameliorated with SGLT2i, making them attractive therapies for HFpEF^{5,13-15}. In addition to uncertain benefit, current therapies for HFpEF have clear potential to cause side effects, such as hyperkalemia, hypotension and acute kidney injury. In contrast, in EMPA-REG OUTCOME, SGLT2i reduced mortality and HF risk without increasing any of these adverse events⁵. Interestingly, SGLT2i with empagliflozin also reduced the need for loop diuretics, which could help preserve renal function and avoid side effects¹⁶. Empagliflozin also has a surprising neutral effect on the SNS, despite an expected contraction of plasma volume^{17,18}. This has been interpreted to reflect a possible "suppressive" effect on the SNS¹⁷⁻¹⁹. Importantly, although the proportion of patients with HFrEF vs. HFpEF in EMPA-REG OUTCOME or the CANVAS Program is not known, based on the clinical characteristics of the cohort it is likely that both subtypes had large representation in the trial. Based on a strong physiological rationale, the likely proportion of HFpEF patients in EMPA-REG OUTCOME and the CANVAS Program and a large unmet clinical need in T2D-HFpEF patients, in the current study we will include patients with this physiological profile to examine the effect of SGLT2i on natriuresis, renal and systemic hemodynamic and neurohormonal function. In addition, due to similar expectations around the high prevalence of HFrEF in EMPA-REG OUTCOME and the CANVAS Program, a large unmet clinical need in these patients, and the expectation that individuals with HFrEF and volume expansion will respond to SGLT2 inhibition with a significant natriuresis, we will also include HFrEF patients with EF \geq 20% in ERADICATE-HF. We anticipate that that both HFrEF and HFpEF will exhibit an expected natriuretic response and similar directional changes in renal and systemic hemodynamic parameters. Nevertheless, to maximize homogeneity in the ertugliflozin and placebo-treated groups, participants will undergo stratified randomization to assure equal numbers of HFrEF and HFpEF phenotypes in the two groups.

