2.1 Sample size calculation

Sample size: The sample size is based on the primary endpoint of proximal fractional sodium excretion (FE_{Na}), which will be measured using fractional excretion of lithium as a surrogate for proximal sodium handling. Based on preclinical studies, and assuming a baseline FE_{Na} of 22±7, to be able to detect a 40% increase in FE_{Na} with an 80% power and a two-tailed alpha = 0.05, 18 patients per group are required, for a total sample size of n=36. This sample size is similar to those successfully used in previous studies², and sufficient to measure secondary endpoints related to Na⁺ handling^{27,28}, renal function², arterial stiffness, plasma volume⁷, systemic vascular resistance ²⁹ and measures of neurohormonal function^{10,17,18}. Randomization will be stratified to assure equal numbers of HFrEF and HFpEF patients in the ertugliflozin and placebo-treated groups. We anticipate an approximate 50%/50% split in the proportion of participants with HFrEF vs. HFpEF, which will be assessed based on the 2D echo at the time of the baseline physiological testing.

Data Analysis: **The primary outcome** is the difference in proximal sodium reabsorption FE_{Na} (measured using FE_{Li}) with ertugliflozin vs. placebo. **Secondary outcomes** will consist of *within* and *between group* changes in hemodynamic and tubular function parameters and vasoactive mediators in response to combination vs. monotherapy regimens. *Within group* comparisons will be analyzed using repeated measures ANOVA. As in previous work, *between group* comparisons will also be made using a 2-way ANOVA with treatment allocation as the dependent variable. *Post-hoc* analyses will be used to compare means, corrected for multiple comparisons. In pre-specified, exploratory sensitivity analyses, the same endpoints will be examined only in those patients who did not have changes in RAAS inhibitors and/or diuretic agents during the treatment period.

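### Randomisation is stratified by HFrEF/HFpEF, but the SAP gives the stratum no role in the primary mixed model or the baseline table, and no reason: a minor mismatch, without bias, that can be corrected at almost no cost

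*SAP*

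**What the plan says.** Protocol, Introduction and rationale: to make the arms more homogeneous, "participants will undergo stratified randomization to assure equal numbers of HFrEF and HFpEF phenotypes in the two groups". Protocol section 2.1 repeats the commitment: "Randomization will be stratified to assure equal numbers of HFrEF and HFpEF patients in the ertugliflozin and placebo-treated groups". It expects a roughly even split between the phenotypes, "which will be assessed based on the 2D echo at the time of the baseline physiological testing". The introduction separates the phenotypes at an ejection fraction of 45%. Section 2.1 states no cut and section 6.2 names no strata, so 45% as the stratification cut is an inference, though a natural one.

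SAP, Analysis for the primary objective, 1.1: "The covariates will include the visit and treatment-by-visit interaction; due to randomization, a covariate for the main effect of treatment will not be included". The general model assumptions complete the specification: "For the linear mixed-effects models with visit and treatment-by-visit interaction as covariates, a participant-level random intercept will be included". Analyses 1.2, 1.3, 2.3-2.6, 3.1-3.3 and 3.7-3.8 reuse this model.

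The baseline list in SAP item 0 opens with "Age, sex, weight, waist circumference, BMI, HbA1c, hemoglobin, fasting blood glucose" and goes on to race, blood pressure and heart rate, eGFR, UACR and medication. Phenotype and ejection fraction are not in it. The stratum does not enter through subgroups either: "There are no planned subgroup analyses for the primary outcome". The ANOVA text in protocol sections 2.1 and 8 does not mention it.

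**The concern.** A factor used to balance the arms is normally carried into the analysis. Balance by stratum makes the treatment estimate more stable than an unadjusted model assumes. If the factor predicts the outcome, the unadjusted standard error is then too wide and the test rejects too rarely under the null. With 36 patients, avoidable loss deserves attention. A plan may leave the factor out, but it should say why, and the only reason given in 1.1 concerns a different term.

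The second gap needs no modelling. Phenotype is read from an echocardiogram at the same visit as randomisation, so a reader will want to see that the strata came out balanced. The planned baseline table does not show it.

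**Working it through.** **The plan's own figure.** Protocol section 2.1 gives 18 per group for a 40% rise from 22 with SD 7 (0.40 × 22 = 8.8 units), 80% power and two-sided alpha 0.05. The two-sample formula gives n = 2 × (1.960 + 0.842)² × 7² / 8.8² = 9.9, so 10 per group (11 with the t-test). With 18 per group, power is Φ(8.8 / (7 × √(2/18)) − 1.960) = Φ(3.77 − 1.96) = 96.5% (95.6% with the t-test). The stated 18 is not reproduced. That is a separate matter, but it explains why the primary test has room to spare here.

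**Inputs.** From the documents: 18 per arm, even phenotype split (9 per arm-by-stratum cell), SD 7, effect 8.8. Assumed, because the documents give no value: visit correlation r = 0.3, 0.5 or 0.7; phenotype difference of 0 or 1 SD (7 units); SD 7 taken as within phenotype.

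**Formulas (large-sample).** The 1.1 model forces a common baseline mean. Its estimate is the arm difference at follow-up minus b times the arm difference at baseline, where b = C/V, V is the visit variance averaged over the two visits and C is the covariance, as the model sees them. With strata balanced across arms, the phenotype difference cancels from the estimate.
- Reported SE without the stratum: √[V(1 − b²) × 2/18]
- True SE without the stratum: 7 × √[(1 + b² − 2br) × 2/18]
- SE with the stratum: 7 × √[(1 − r²) × 2/18]

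A 7-unit difference in a 50/50 split adds (7/2)² = 12.25 to the variance. If it holds at both visits, V = 49 + 12.25 = 61.25 and C = 49r + 12.25. If it holds only at follow-up, V = (49 + 61.25)/2 = 55.125 and C = 49r.

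| Shift | r | b | Reported SE, no stratum | True SE, no stratum | SE with stratum |
|---|---|---|---|---|---|
| Both visits | 0.3 | 0.44 | 2.34 | 2.25 | 2.23 |
| Both visits | 0.5 | 0.60 | 2.09 | 2.03 | 2.02 |
| Both visits | 0.7 | 0.76 | 1.70 | 1.67 | 1.67 |
| Follow-up only | 0.3 | 0.27 | 2.39 | 2.23 | 2.23 |
| Follow-up only | 0.5 | 0.44 | 2.22 | 2.03 | 2.02 |
| Follow-up only | 0.7 | 0.62 | 1.94 | 1.68 | 1.67 |

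The true SE is almost the same with and without the stratum. What changes is the reported SE, which is too wide without it.

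**Simulation of the REML model** (t reference with 34 or 33 df; results for r = 0.3 / 0.5 / 0.7 where three are given):
- No phenotype effect: adding the stratum costs no precision (SE ratio 1.000-1.001).
- Equal 1 SD shift: type I error 4.2-4.8% without the stratum. Power at 8.8 units without and with it: 96.4 vs 97.5%, 98.7 vs 99.0%, 99.9 vs 99.9%.
- Follow-up-only 1 SD shift: type I error 2.2-3.8% without the stratum. Power at r = 0.3: 96.0 vs 97.3%, the largest gap in any setting.
- With the stratum, type I error is about 5.0-5.4%.
- Bias without the stratum is at most 0.07 units, which is simulation noise.

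**Outcomes tied to ejection fraction.** A cut in a continuous ejection fraction truncates the baseline variance within each stratum but not the follow-up variance in the same way, whereas the random-intercept model assumes the two are equal. With ejection fraction assumed normal and cut at its mean, and r = 0.7, type I error with the stratum was 7.8% for an outcome correlating 0.9 with ejection fraction and 7.2% at 0.8, against 5.1-5.3% without. A smaller run gave 7.4% and 6.2%, and only 5.6% at a correlation of 0.6. If ejection fraction instead fell into two separated groups, ejection fraction itself as the outcome gave 5.0-5.1%. The inflation therefore depends on a distribution that the documents do not give.

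**The case against.** The case for leaving the model alone is strong on size. Nothing is biased, type I error is not inflated by the omission, and the design effect is detected with about 96% power or more either way. The stated purpose of stratifying is homogeneous arms, which the allocation delivers without a model term. The lowest error rates need the phenotypes to be level at baseline and 7 units apart at follow-up with no drug effect. That is hard to square with required stable background doses and with the protocol's expectation that both phenotypes respond in the same direction. All of this stands, and it makes the point minor.

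It does not remove the point, because the omission is unexplained and adding the terms costs no precision for FE(Li). The margin also shrinks if the true effect is smaller. At an effect giving about 80% power, omission costs 1-4 points for an equal 1 SD shift and 5-11 points for a follow-up-only 1 SD shift.

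Three stronger readings are tempting.
- A reader might infer that the primary test is invalid or biased. It is not: the error is on the conservative side.
- A reader might infer that adjustment matters most for the echocardiographic measures in SAP 2.4, where the phenotypes differ most. The documents do not support this. The stratum is defined by ejection fraction, the individual echocardiographic measures are not listed, and the added terms can make the test anti-conservative there. Excluding ejection fraction alone would not be enough.
- A reader might infer that balance could never be checked. Echocardiography is done at Visit 3 and analysed under 2.4, so baseline ejection fraction by arm may appear there; the SAP does not promise it.

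**Conclusion.** The point holds as a minor mismatch between design and analysis. The stratum has no role in SAP 1.1, in the models that copy it or in item 0, and no reason is given. The treatment estimate is unbiased, provided that the stratified allocation was carried out and that data are missing at random given the model; dropout depending on both phenotype and arm was not examined. The consequence for the primary test is mild conservatism if phenotype affects FE(Li), and about 1 point of power at 8.8 units. The sizes rest on assumed phenotype shifts and visit correlations. The direction does not, as long as the strata are balanced across arms and the outcome is not closely tied to ejection fraction.

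**What to change.** - In SAP 1.1 for FE(Li), and in 1.2 and 1.3 for the sodium-handling outcomes, add HF phenotype as randomised and phenotype-by-visit as fixed effects. Alternatively, keep the unadjusted model as primary, state the reason, and report the stratum-adjusted model as a sensitivity analysis.
- Add HF phenotype and baseline ejection fraction, by arm, to the item 0 baseline table.
- State that the stratum terms do not pass automatically to the other analyses that copy 1.1, in particular echocardiographic measures and any outcome closely correlated with ejection fraction.

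The cost is SAP wording. The variable already has to exist for randomisation. The terms use 1-2 degrees of freedom in each two-visit model and one more parameter in 1.3.
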